5.2 Schedule

The Investigator is responsible for completing the cohort summary template and submitting to the IND office Medical Monitor for review and approval prior to advancing subjects to the next protocol specified cohort/dose level. A copy of the cohort summary should be placed in the Investigator's Regulatory Binder under "sponsor correspondence". This should be submitted after the first six patients.

5.2.1 Patients will be treated according to the following schedule:

- 5-azacytidine will be administered subcutaneously (SQ) or intravenously (IV) for 7 days of every cycle with daily schedule of 7 consecutive days (Days 1-7) or for days 5-2-2 which is 5 consecutive weekdays (Days 1-5) with rest on the 2 weekend days (Days 6 and 7) and then dosing the first two weekdays of the next week (Days 8 and 9) of each 28-day cycle as determined by treating physician. Alternative dosing schedules such as 4-2-3 which is 4 consecutive weekdays (Days 1-4) with rest on the 2 weekend days (Days 5 and 6) and then dosing the first three weekdays of the next week (Days 7, 8, and 9) of each 28-day cycle or other schedules allowing the 2 day weekend interruption may be applied as long as we make every attempt to give the 7 days of azacytidine as consecutively as possible. This must be clearly documented in the medical record as determined by treating physician after approval from the PI. Both SQ

and IV forms of administration are FDA approved and considered interchangeable. Patients may start receiving 5-azacytidine by one route and changed to the other, and also administration schedules from one schedule and changed to the other at any time as needed based on patient and/or physician preference.

- Avelumab will be administered as an approximately 60 minute (+/- 30 minutes) IV infusion on Day 1 and day 14 (+/-3 days) of each 5-azacytidine cycle for the first 4 cycles or until CR (whichever occurs earlier) followed by a maintenance regimen (one dose of avelumab on day 1 of each cycle of 5-azacytidine). Patients who have evidence of budding relapse or seem to have clinical benefit may continue or revert back to receiving avelumab on Day 1 and day 14 (+/-3 days) of each cycle of 5-azacytidine. Patients may receive avelumab more or less frequently during the maintenance regimen only after discussion with the PI. Avelumab will be administered every cycle with no interruptions unless there are adverse events as described in Section 5.3.

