- 5.2.1.4 We will first treat 6 patients at dose level -1 in the lead-in phase IB. If DLT occurs in $\geq 2/6$ patients, this dose level would exceed the MTD, and 6 patients will be treated at the next lower dose level (i.e. dose level -2). If DLT occurs in $< 2/6$ patients, this dose level would not exceed the MTD, and 6 patients will be treated at the next higher dose level (i.e. dose level 0). The dose de-escalation (Table 1) will continue in cohorts of 6 until we reach the maximum dose level at which $< 2/6$ patients experience a DLT in the first 28 days. The maximum dose level at which 0-1/6 patients experience a DLT in the first 28 days of treatment will be the MTD in this study and will be used to treat an additional 40 patients in the phase II portion of the study. If $\geq 2/6$ patients experience DLT at dose level -3, the study will be revised to consider additional lower dose levels (based on potential synergistic toxicity).
- 5.2.1.5 If DLT is observed in the first 28 days of treatment in 0 or 1/6 at dose level 0, then dose level 0 will be used for the phase II portion of the study.
- 5.2.1.6 Patients must receive a total of 7 doses of azacytidine and 2 doses of avelumab during the first 28 days on trial (i.e. during cycle 1) to be evaluated for DLT. Patients may have up to a total of 7 days interruption in the azacytidine dosing during the first 28 days and still be evaluable for DLT if the interruption is for complications or hospitalizations NOT related to the azacytidine or the avelumab. Patients who receive less than 7 doses of azacytidine and/or less than 2 doses of avelumab during the first 28 days on trial will NOT be evaluable for DLT. Patients not evaluable for DLT will be replaced. These patients may continue therapy on trial after discussion with the PI if they are having clinical benefit or if in the best interest of the patient and the reasons for continuation and potential benefit/risk profile for the patient must be clearly documented in the medical records.
- 5.2.1.7 Once MTD is defined, the RP2D will be selected based on efficacy and safety result from the phase I in discussion with the PI and the sponsor. The Investigator is responsible for completing the cohort summary template prior to advancing subjects to the phase II portion. Any patients still on study from the phase I portion at a dose lower than RP2D can be dose escalated up to RP2D. However, the dose for any patient may never exceed the RP2D.

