11.2 Statistical Design

Part a. Lead-in phase IB

The MTD is defined as the highest dose level with ≤ 1 out of 6 patients experience a DLT during the first 28 days of treatment. DLT is defined in section 5.2.2. The dosing schema for the combination treatment during the lead in phase is shown in Table 1 in section 5.2.1.

A Toxicity Summary will be submitted to the IND Office Medical Monitor, after the first three evaluable patients have completed their first cycle, and every three evaluable patients thereafter, prior to dose modification, expansion, or phase II initiation.

Part b. Phase II

An Efficacy/Toxicity Summary will be submitted every five evaluable patients during Phase II.

The historical experience in relapsed/refractory AML patient population is that historical responses (CR/CRp/CRi/PR/Hi/MLFS with >50% blast reduction) with single agent hypomethylator therapy (5-azacytidine or decitabine) or with hypomethylator combinations (azacytidine+revlimid, decitabine+myelotarg, azacytidine+vorinostat, decitabine+valproate) investigated at MDACC over the last 10 years are 10% ([name], Kantarjian H et al., European Hematology Association Conference, June 2016). The target ORR with the experimental treatment is 30%. This regimen of the combination treatment will be considered worthy of further investigation if it elicits an increase in ORR to 30% with acceptable toxicity. A >30% drug-related grade 3/4 toxicity rate is considered unacceptable. Thus, interim monitoring rules, assuming the prior distributions above, were constructed that meet the following two conditions,

- 1) Stop if $\text{Prob}\{p(\text{ORR}, E) < p(\text{ORR}, H) + 0.20 \mid \text{data}\} > 0.975$, or
- 2) Stop if $\text{Prob}\{p(\text{TOX}, E) > 0.30 \mid \text{data}\} > 0.975$,

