All patients who received any dose of the study agent will be included in the analysis for efficacy and safety. Demographic/clinical characteristics (including duration of response) and safety data of the patients will be summarized using descriptive statistics such as mean, standard deviation, median and range. For the primary efficacy analysis, we will estimate the ORR for the combination treatment, along with the 95% credible interval. For the efficacy, a sample size of 40 patients ensures a posterior 95% credible interval for ORR of (0.17, 0.43), if the trial is not terminated early, under the assumption of a 30% ORR. Patients who drop out of the study before completing all the cycles will be treated as “failures” for the primary analysis. ORR during the study period will also be presented with the 95% confidence credible. The association between ORR and patient’s clinical characteristics will be examined by Wilcoxon’s rank sum test or Fisher’s exact test, as appropriate. Toxicity type, severity and attribution will be summarized for each patient using frequency tables.

The distribution of time-to-event endpoints (DFS and OS) including overall survival and progression free survival will be estimated using the method of Kaplan and Meier. Comparisons of time-to-event endpoints by important subgroups will be made using the log-rank tests. Paired t-tests will be used to determine the immunological and molecular changes in the peripheral blood and bone marrow from baseline to the time of response, and to the time of disease progression. Correlation analysis (such as logistic regression analysis) will be conducted to determine the relationship between induction of hypomethylation / DNA damage and clinical response.

A Toxicity Summary will be submitted to the IND Office Medical Monitor, after the first three patients have completed their first cycle of study therapy or administration is

discontinued, whichever comes first, and every three evaluable patients thereafter during the Lead-in Phase IB.

An Efficacy/Toxicity Summary will be submitted every five evaluable patients during **Phase II**.

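### Section 5.2.1.6 makes no exception for a lead-in patient whose DLT caused the missed dose, so read literally that DLT drops out of the 0-1/6 MTD count and the patient is replaced

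*Combined protocol and SAP*

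**What the plan says.** **Evaluability (5.2.1.6).** To be evaluated for DLT, a lead-in patient must receive 7 azacytidine doses and 2 avelumab doses in the first 28 days. Those with fewer than 7 azacytidine doses and/or "less than 2 doses of avelumab during the first 28 days on trial will NOT be evaluable for DLT". The one tolerance is up to 7 days of azacytidine interruption, and only "if the interruption is for complications or hospitalizations NOT related to the azacytidine or the avelumab". The consequence is stated flatly: "Patients not evaluable for DLT will be replaced".

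**MTD rule (5.2.1.4, repeated in 11.2).** "The maximum dose level at which 0-1/6 patients experience a DLT in the first 28 days of treatment will be the MTD". A level with 2 or more DLTs in 6 exceeds the MTD.

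**What a DLT is (list following 5.2.1.3).** It includes any treatment-related death and, with exceptions, clinically significant Grade 3 or 4 non-hematologic events.

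**What happens to dosing after such events.** Table 5 and section 6.1.5 end study drug after a Grade 3 or 4 infusion reaction. Table 3 discontinues avelumab for Grade 3-4 diarrhea/colitis and for Grade 3-4 pneumonitis. Section 5.3.4 discontinues avelumab for Grade 3 and Grade 4 events, with listed exceptions.

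**The concern.** The evaluability rule should remove patients who were too lightly exposed to tell us whether the dose is tolerable. A patient who stops because of a DLT has already given that answer. As written, the rule does not separate the two. Its only relief is for interruptions unrelated to study drug, so a dose lost to drug toxicity gets none.

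The 0-1/6 count decides whether the next six patients move from level -1 (avelumab 3.0 mg/kg) to level 0 (10.0 mg/kg). Its result also carries to 40 further patients in Phase II. A rule that can drop the events it exists to count makes a level look safer than it would if those events were counted.

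**Working it through.** **1. The plan's own lead-in figure.** The cohort-of-6 paths in 5.2.1.4 are: level -1 then 0, 12 patients; level -1 then -2, 12 patients; levels -1, -2 and -3, 18 patients. This reproduces the 12-18 in section 11.1 and, with 40 Phase II patients, the total of 52-58. The figure includes no replacements. The plan gives no operating characteristics for the 0-1/6 rule.

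**2. The passages together.** A treatment-related death before avelumab dose 2 is a DLT by definition, and the patient cannot reach 2 doses. A Grade 3/4 reaction to the first infusion bars further study drug, so the patient again cannot reach 2 doses. Grade 3-4 colitis or pneumonitis before dose 2 stops avelumab under Table 3, with the same result. In each case 5.2.1.6 declares the patient non-evaluable and replaces them. No section says that a patient with a DLT stays evaluable.

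**3. Example that needs no assumed rate.** Among the first six patients, one has a Grade 4 reaction to the first infusion and one has a DLT after all required doses.
- As written: the first is replaced; if the replacement has no DLT, the count is 1/6 and the level passes.
- If every DLT counted: 2/6, and the level exceeds the MTD.

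**4. Direction.** Hold the order of enrolment fixed and start from six places filled with every DLT counted. The written rule removes *k* DLT patients who missed a dose and fills their places with *k* later patients, who add at most *k* DLTs. The written count is therefore never higher. Every level that passes with all DLTs counted also passes as written, but not the reverse. So the difference between the two pass probabilities is the probability of a changed decision.

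**5. Possible size (illustration only).** Let *p* be the true DLT rate and *f* the share of DLTs that cost a required dose. Neither is in the documents; both are assumed. Assume also that no patient without a DLT misses a dose.
- DLT rate among evaluable patients as written: q = p(1 - f)/(1 - pf).
- Chance of passing: (1 - q)^6 + 6q(1 - q)^5.
- For example, p = 0.30 and f = 0: 0.1176 + 0.3025 = 0.420. With f = 0.50: q = 0.15/0.85 = 0.176 and the chance of passing is 0.713.

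| True DLT rate | Pass, f = 0 | f = 0.25: q, pass | f = 0.50: q, pass | Changed decision, f = 0.25 / 0.50 |
|---|---|---|---|---|
| 20% | 0.655 | 0.158, 0.758 | 0.111, 0.863 | 0.10 / 0.21 |
| 30% | 0.420 | 0.243, 0.550 | 0.176, 0.713 | 0.13 / 0.29 |
| 40% | 0.233 | 0.333, 0.351 | 0.250, 0.534 | 0.12 / 0.30 |

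The last column is pass(f) minus pass(0).

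**The case against.** **Others will see these events before the dose is chosen.** This largely stands. The cohort summary goes to the Medical Monitor "for review and approval prior to advancing subjects to the next protocol specified cohort/dose level". Under the Statistical Analysis Plan text the first toxicity summary is due "after the first three patients have completed their first cycle of study therapy or administration is" discontinued, so a patient who stopped early is visible. Section 11.2 calls for further summaries "every three evaluable patients thereafter, prior to dose modification, expansion, or phase II initiation". Section 5.2.1.7 adds: "Once MTD is defined, the RP2D will be selected based on efficacy and safety result from the phase I". Section 5.4.2 keeps anyone who received a dose evaluable for toxicity. These are real safeguards, but the reviews rest on judgement, and 5.4.2 does not mention DLT or the MTD count. None of them changes the written count.

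**Phase II has a numeric toxicity rule.** Table 7 stops accrual at, for example, 4 of 5 or 7 of 10 patients with drug-related Grade 3/4 toxicity. Table 9 puts the chance of early stopping at 0.45 and 0.78 for true toxicity rates of 40% and 50% when the ORR is 30%. This limits later harm, but only after the dose has been chosen.

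**The MTD rule says patients, not evaluable patients.** Sections 5.2.1.4 and 11.2 leave out that word, and the remark in 5.2.1.6 about replaced patients continuing for benefit fits those who missed doses for other reasons. A team might therefore count the DLT in practice. But 5.2.1.6 is the specific rule and is categorical, so doing so would depart from the text.

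**Not every early DLT costs a dose.** This stands. Section 5.3.3 lists several events for delay with later resumption, and Table 3 allows delay for some rash and endocrine events. Some patients could still receive dose 2 by day 28, and a DLT after all required doses is always counted.

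**The illustration assumes that DLT-free patients never miss doses.** This also stands. If a share *g* of them does, the written rate becomes p(1 - f)/[p(1 - f) + (1 - p)(1 - g)]. With g = f this equals *p*, and the chance of passing at 30% is 0.42. A reader might infer that the counted rate always lies below the true DLT rate. The documents do not support that: with g above f it lies above. What holds whatever *g* is, is the comparison in step 4.

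**Conclusion.** The rule is wrong as written, not merely short of detail. Read literally, 5.2.1.6 excludes from the 0-1/6 count any DLT that itself costs a required dose, and the written count can then never exceed the count with such events included. The two-patient example shows that a level can change from exceeding the MTD to passing.

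The wording gap and its direction are firm. The size is not: changed-decision chances of 0.10 to 0.30 rest on an assumed *f* of 0.25 or 0.50, true DLT rates of 20% to 40%, and no missed doses among DLT-free patients. A lower *f*, for instance where events only delay dosing, makes them smaller.

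A reader might also infer that all early DLTs are lost, or that too high a dose would go forward unnoticed. Neither follows, given the delay provisions and the reviews that precede dose selection.

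**What to change.** In 5.2.1.6, state that any lead-in patient who received at least one dose of either drug and has a protocol-defined DLT in the DLT period is evaluable and counts as a DLT, whatever number of doses was received. State that only patients without a DLT who miss required doses are replaced. List each replaced patient, with the reason, in the cohort summary that section 5.2 already requires.

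**Cost.** Two sentences of text and one listing. Levels may fail somewhat more often, which can move the lead-in from 12 towards the planned 18 patients. If DLT-free patients also miss doses, the new count leans conservative: setting f = 0 in the formula with *g* gives p/[p + (1 - p)(1 - g)], which is above *p*. That is an acceptable direction for a safety lead-in.

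**Separate, secondary items to reconcile only.** (i) The DLT list includes Grade 4 neutropenia lasting at least 42 days and refers to the first cycle, and section 3.0 describes a lead-in cycle of at least 28 days. Sections 5.2.1.4, 5.2.2.1, 5.2.2.4, 11.1 and 11.2 use 28 days. (ii) Section 5.3.3 lists for delay some Grade 3 events that 5.3.4, with exceptions, lists for discontinuation. No clinical rule is proposed for either.

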5.3 Dose Adjustments

5.3.1 Avelumab and 5-azacytidine dose adjustments for hematological drug-related adverse events (AE):

Dose reduction/interruption/discontinuation decisions should be based on the

CTCAE version 4.03 (**Appendix E**) and the guidelines provided below.

Patients with acute leukemia's usually present with abnormal peripheral blood counts at the time therapy is started and myelosuppression is an expected event during the course of therapy for acute leukemia. Thus, no dose adjustments or treatment interruptions for myelosuppression will be planned for the first 4 cycles and/or in the presence of residual leukemia. After that, treatment interruptions and dose adjustments may be considered according to the following guidelines only when there is no evidence of active leukemia (e.g., only if <5% blasts in the bone marrow or cytopenias not considered to be related to leukemia).

- Patients with a response (no marrow evidence of leukemia) and pre-cycle counts of neutrophils $>1 \times 10^9/L$ and platelets $>50 \times 10^9/L$ who have sustained low counts of neutrophils $<0.5 \times 10^9/L$ or a platelet count $<20 \times 10^9/L$ for more than 2 consecutive weeks in the current cycle, may have the treatment with 5-azacytidine interrupted at the discretion of the treating physician after discussing with the PI until neutrophils recover to $\geq 1 \times 10^9/L$ and platelets to $\geq 50 \times 10^9/L$.
- If there are persistent peripheral blood blasts, or the bone marrow shows $>5\%$ blasts or evidence of residual leukemia, treatment may be continued regardless of neutrophil and platelet count with supportive care as needed. Dose-interruptions of 5-azacytidine in these patients should be considered on an individual case-by-case basis and discussed with the PI.
- Investigators should, whenever possible, determine which medication is causing the toxicity and interrupt or dose reduce 5-azacytidine and/or interrupt avelumab, as applicable. No dose reductions (only dose interruptions as needed) are permitted for avelumab in the phase II portion after RP2D has been established. Avelumab has not been associated with neutropenia and/or thrombocytopenia in prior studies and should generally not be interrupted or discontinued for myelosuppression.

5.3.2 5-azacytidine dose adjustments for non-hematologic drug-related AEs

Investigators should, whenever possible, determine which medication is causing the toxicity and interrupt or dose reduce 5-azacytidine and/or interrupt avelumab, as applicable. No dose reductions (only interruptions) are permitted for avelumab in the phase II portion after RP2D has been established.

Dose reductions of azacytidine [to be implemented in the phase II portion of the study](#) will be as follows: dose level -1 of azacytidine: 50 mg/m², dose level -2: 37.5 mg/m², dose level -3: 25 mg/m².

Table 2 Dose adjustments of azacytidine for non-hematologic drug-related AEs, clinically significant in the opinion of the investigator

Grade	Occurrence	Dose modification
1 or 2	Any time	No dose reduction
3 or 4 (Persistent grade 2: Consider similar dose adjustments if persistent and not responding to optimal management in the opinion of PI and treating physician)	1st and 2nd time	Hold 5-azacytidine. Resume 5-azacytidine at prior dose if recovery to \leq Grade 1 occurs within 14 days. If toxicity persists for 15-28 days, hold therapy and resume 5-azacytidine at prior dose if recovery to \leq Grade 1 OR resume 5-azacytidine at ONE dose level below current dose if recovery to \leq Grade 2. Dose re-escalation to prior dose of 5-azacytidine is permitted in accordance with the dose-escalation guidelines in section 5.3.6.
	3 rd and 4th time	Hold 5-azacytidine. Follow until toxicity \leq Grade 2. Resume 5-azacytidine at ONE dose level below current dose. Dose re-escalation of 5-azacytidine to prior dose is permitted in accordance with the dose-escalation guidelines in section 5.3.6..
	5th time	Discontinue therapy

5.3.3 Avelumab dose delay/interruption for immune-oncology drug-related AEs, clinically significant in the opinion of the investigator

Avelumab administration should be delayed for the following drug-related AEs, clinically significant in the opinion of the investigator:

- Any Grade \geq 2 non-skin AE, except that
 - Grade 2 fatigue or laboratory abnormalities do not require delay, however
 - Patients with ALT or AST > 3 and up to 5 x ULN or total bilirubin greater > 2.0 mg/dL and up to 3 x ULN or creatinine > 2.0 mg/dL and up to 3 x ULN should have avelumab treatment withheld.

Avelumab administration should be delayed for the following drug-related AEs, clinically significant in the opinion of the investigator:

- Any Grade 3 skin AE, or Grade 3 laboratory abnormality, with the following exceptions:
 - Grade 3 lymphopenia or leukopenia does not require dose delay.
 - However, patients with ALT or AST > 5 x ULN or total bilirubin greater > 3 x ULN or creatinine > 3 x ULN should have avelumab treatment interrupted.
- Any AE, laboratory abnormality, or intercurrent illness, which in the judgment of the investigator, warrants delaying the dose of study medication.
- Avelumab dose reductions are not permitted in this study (only dose delays when indicated).

Subjects may resume treatment with study drug when the drug-related AE(s) resolve to Grade ≤ 1 or baseline value, with the following exceptions:

- Subjects may resume treatment in the presence of Grade 2 fatigue
- Subjects who have not experienced a Grade 3 drug-related skin AE may resume treatment in the presence of Grade 2 skin toxicity
- Drug-related pulmonary toxicity, diarrhea, or colitis, must have resolved to baseline or at least \leq grade 1 before treatment is resumed
- Drug-related endocrinopathies adequately controlled may resume treatment

If the criteria to resume treatment are met, the subject should restart treatment at the next scheduled time point per protocol. However, if the treatment is delayed past the next scheduled time point per protocol, the next scheduled time point will be delayed until dosing resumes. Patients who receive combination therapy in whom continuation of 5-azacytidine is considered to be inadequate, or inappropriate (e.g., because of pancytopenia) can discontinue 5-azacytidine and continue with avelumab only.

If treatment is delayed > 8 weeks, the subject must be permanently discontinued from study therapy, except as specified in discontinuation section.

